1.1. Overall aims

The overarching objective of Our Future Health is to help people live healthier lives for longer through better prevention, earlier detection and improved treatment of diseases. The Our Future Health research programme will speed up the discovery of new methods of early disease detection, and the evaluation of new diagnostic tools, to help identify and treat diseases early when outcomes are usually better.

To achieve these objectives, we will recruit up to 5 million adults from across the UK to create a diverse and inclusive cohort of people who have consented to participate in the research. In addition to being asked for permission to link their personal health data to other health-relevant data, participants will be asked to provide biological samples and complete questionnaires on recruitment; agree to re-contact for ongoing biological sampling and questionnaires and consider taking part in further research studies; and agree to being offered personal health information arising from the research. The specific aims are presented below.

- **Specific Aim 1:** Build a resource linking multiple sources of health and health-relevant information, including genetic data, on millions of people in the UK, to facilitate basic discovery research by academic and commercial researchers on early indicators of disease
- **Specific Aim 2:** Analyse the data in the resource to estimate personal disease risk information for participants, based on genetic and non-genetic information, and offer this estimated personal health information to participants
- **Specific Aim 3:** Re-contact sub-groups of participants generally for additional samples, and additional data collection including linkage to digital data sources
- **Specific Aim 4:** Re-contact participants on a risk-stratified basis (i.e. recall-by-genotype/phenotype or sociodemographic characteristics) over time specifically to enable secondary studies by academic and commercial researchers that are greatly enhanced by being able to identify highly enriched sub-populations/sub-cohorts of participants

Building this large resource with linkage, feedback and re-contact will facilitate a new generation of discovery and translational research that will advance the development and testing of early diagnostic technologies and preventive (or ‘personalised precision health’) interventions.

The UK is uniquely placed to deliver this programme. We have an exceptional track record in population research, and many outstanding research groups. Our diverse (ethnically/socioeconomically) population is willing to take part in research. Our government is committed to levelling up the major inequalities in health outcomes seen across the population. The NHS and our comprehensive disease registration systems provide a mechanism for invitation, recruitment and follow-up at an unprecedented size and scale. In addition, a programme of this scale and nature is made possible by the major advances in digital technologies over the past decade. Furthermore, the proportion of the UK public connected to data and devices (‘digital health’) is substantial and rapidly growing.

The Our Future Health research programme is intended to be both a prospective observational cohort and a platform for future discovery and translational research studies with consent for return of results, risk-stratification, and re-contact. Our Future Health will build on our national

strengths and complement existing prospective cohort resources and translational research efforts in the UK.

1.2. Genesis of Our Future Health

The initial idea to set up a very large cohort in the UK to improve early detection of chronic diseases was first discussed in 2016, when several medical research charities (including Cancer Research UK), the Medical Research Council, and leading public health practitioners and academics started exploring the rationale. The concept was described in the 2017 Life Sciences Industrial Strategy and discussions progressed on possible government funding.

The proposal to establish a 5-million strong volunteer cohort enabling research intended to improve the early detection of chronic diseases was set out in the Accelerating Detection of Disease challenge of the government's Industrial Strategy Challenge Fund (ISCF).

An investment of £79 million was allocated from the ISCF by UK Research and Innovation to test the feasibility of, and establish, the Our Future Health research programme. This was expected to be matched by funding of at least £160 million from industry and charity partners who would work in partnership with Our Future Health to design and deliver the programme.¹

1.3. Initial planning of Our Future Health

In 2018, a Science Task & Finish Group was convened to make recommendations on the scientific design / scientific protocol of Our Future Health (Successive Chairs: [name]; [name], [name]). The Science Task & Finish Group concluded its work in early 2020.

An Ethics and Feedback Advisory Group (EFAG) was established in Sept 2019 to provide strategic advice on the development of ethical guidelines and principles for Our Future Health, and to develop an Ethics and Governance Framework to guide its operations (Successive Chairs: [name]; [name]). The first draft of this Framework (completed in Oct 2020) provides advice to the Board and Executive, and will be publicly available for funders, partners, researchers, participants and the general public. Building on the work of EFAG, an Ethics Advisory Board has been established as part of the long-term governance of the cohort and is responsible for monitoring the implementation of the Ethics & Governance Framework, and for reviewing and updating it as appropriate.

An Industry Advisory Group and an NHS Advisory Group were established early on in the development of the programme. Further details regarding governance structures being put in place can be found at the end of this document.

In Sept 2019, a not-for-profit company was established to run Our Future Health. The company, initially named Early Disease Detection Research Project UK (EDDRP UK), was registered as a charity in May 2020. The Executive was established in April-May 2020 with [name] as the CEO. The programme was subsequently renamed from the placeholder EDDRP UK to Our Future Health in 2021.

¹ <https://www.ukri.org/innovation/industrial-strategy-challenge-fund/accelerating-detection-of-disease/>

2. Scientific rationale

2.1. Prospective study design

Prospective observational cohort studies are valuable because these real-world studies facilitate the identification of biomarkers and causative factors that contribute to future disease.² Prospective study designs are less prone to bias than case-control study designs.

Existing large prospective studies in the UK and Europe include:

- **UK Biobank:** 500,000 participants, UK³
- **Million Women Study:** 1.3 million participants, England and Scotland⁴
- **Whitehall I and II Studies:** 17,500 and 10,000 participants respectively, England^{5,6}
- **ALSPAC:** Avon Longitudinal Study of Parents and Children, 14,000 families, England⁷
- **Understanding Society:** The UK Longitudinal Household Study, 40,000 households, UK⁸
- **GLAD Study:** Genetics Links to Anxiety and Depression, n=22,000 to date (aim is 40,000), UK⁹
- **EPIC:** European Prospective Investigation of Cancer and Nutrition, 500,000 participants, UK and 9 countries in Europe¹⁰
- **Genes and Health:** 50,000 participants (aim is 100,000), UK¹¹

There are a number of large or influential prospective studies in the US, including:

- **All of Us** (currently have recruited ~350,000 participants; aiming to achieve a final sample size of 1 million, US)¹²
- **Million Veteran Programme** (1 million participants, US)¹³
- **Nurses Health Study** (275,000 participants, US)¹⁴
- **Framingham Heart Study** (originally 5,000 participants, US)¹⁵

Prospective studies with East Asian and Hispanic populations have also been set up, including the following which are collaborations with investigators at Oxford University:

- **Kadoorie Study** (500,000 participants, China)¹⁶
- **Mexico City Prospective Study** (150,000 participants, Mexico)¹⁷

² Manolio et al (*Nature Reviews Genetics*, 2006) Genes, environment and the value of prospective cohort studies. <https://pubmed.ncbi.nlm.nih.gov/16983377/>

³ <https://www.ukbiobank.ac.uk/>

⁴ <http://www.millionwomenstudy.org/introduction/>

⁵ van Rossum et al (*J Epidemiol Community Health*, 2000) Employment grade differences in cause specific mortality. A 25 year follow up of civil servants from the first Whitehall study. <https://www.ncbi.nlm.nih.gov/pmc/articles/PMC1731642/>

⁶ <https://academic.oup.com/ije/article/34/2/251/746997>

⁷ <http://www.bristol.ac.uk/alspac/about/>

⁸ <https://www.understandingsociety.ac.uk/>

⁹ <https://gladstudy.org.uk/about/>

¹⁰ <https://epic.iarc.fr/>

¹¹ <https://www.genesandhealth.org/>

²⁰ Peters, Taghreed, Olakunle, Akua, Nhan. Implementation research: what it is and how to do it BMJ 2013; 347:f6753 <https://www.bmj.com/content/347/bmj.f6753.full>

²¹ Sharpe et al (2020) The early landscape of coronavirus disease 2019 vaccine development in the UK and rest of the world <https://onlinelibrary.wiley.com/doi/full/10.1111/imm.13222>

²² <https://www.genome.gov/Funded-Programs-Projects/Electronic-Medical-Records-and-Genomics-Network-eMERGE>

In the UK, examples of individual translational research studies that are embedded within public health programmes at a national scale include:

- A study examining uptake of colorectal cancer screening over three invitation rounds in the NHS Bowel Cancer Screening Programme among individuals aged 60-64yrs (n=62,000)²³
- A randomised controlled trial (UK Age trial) investigating the effect of mammogram breast screening from age 40 years on breast cancer mortality involving 23 breast screening units across Great Britain (n=161,000)²⁴
- A study of the effectiveness of NHS Health Check programme at reducing cardiovascular disease risk among patient aged 40-74 years after one year (n=3,172)²⁵

The intent is that Our Future Health research programme will provide both a:

- (1) **Prospective observational dataset** for basic science / epidemiological, discovery and aetiological research e.g. on the causes and early signs of disease; and
- (2) **Translational research platform** comprising a cohort of people who can be re-contacted for translational/implementation research to develop and test new diagnostic technologies, prevention strategies and treatments.

Our ambition is to recruit an ethnically and socioeconomically diverse population. We expand further on this important point in the sample frame section below.

2.3.1. Sample frame ambition

The 5 million participants we aspire to recruit into Our Future Health will be reflective of the UK population according to the most recent census data available. To inform such, we have drawn on 2011 census data of population counts by age, sex, ethnicity, and index of multiple deprivation for England and Wales, Scotland, and Northern Ireland. We will update our sample frame with census 2021/22 when they become available in late 2022 and 2023.

Table 1. Sample frame ambition

Sex >	Female				Male			
Ethnicity >	White	Black	Asian	Mixed/Other	White	Black	Asian	Mixed/Other
Age >								
v								
18–19	68,090	3,360	6,755	3,859	69,687	3,308	7,068	3,968
20–29	354,596	16,074	45,872	16,666	353,073	14,744	47,995	18,184
30–39	347,493	17,760	44,405	12,902	343,187	15,893	44,993	14,818
40–49	416,477	18,376	28,215	9,369	406,695	16,686	27,690	10,168
50–59	356,575	9,130	19,971	4,972	350,377	8,091	19,132	5,337
60–69	331,220	4,114	11,255	2,609	317,787	2,982	9,516	2,639
70–79	229,045	3,419	6,365	1,433	195,353	3,075	6,536	1,384
80–84	85,797	799	1,479	421	59,129	702	1,332	372
85+	92,450	442	953	346	43,752	358	684	242
Totals	2,281,742	73,474	165,270	52,577	2,139,040	65,840	164,946	57,110
%	45.6%	1.5%	3.3%	1.1%	42.8%	1.3%	3.3%	1.1%

This sample frame ambition is reflective of the UK population in terms of age, sex, and ethnicity. It will provide large numbers of participants of the primary ethnic minority groups resident in the UK – Indian, Pakistani, Bangladeshi, Chinese, Black African, Black Caribbean, Arab and Mixed – populations that have been underrepresented in health research. Combined with a proportional representation of participants across the nations, this sample frame will provide for a diverse cohort that will be amenable to a variety of studies that have not been possible in a UK prospective cohort before.

Achieving a sample that is reflective of the UK population is an overarching aim of the Our Future Health programme for both ethical and scientific reasons. Ethically, it is important that we make substantial efforts to make participation in Our Future Health equitable and accessible to people regardless of their socioeconomic position, disability, physical health, mental health, sex, age, and ethnicity. Scientifically, it is important that the participants in Our Future Health are sufficiently diverse to facilitate a range of discovery and translational research the resource is intended to support. Related to this, the concept of “representativeness” has been debated at length in the

epidemiologic literature^{26,27}. We recognise that our participant sample is unlikely to be fully representative of the UK population in a large range of demographics and risk factors that extend beyond those shown in Table 1. However, the important aspects of representativeness and selection biases are specific to any hypothesis being tested and the external population to which an inference is to be made²⁸. By ensuring we recruit a diverse population, we will provide a resource that is amenable to a large range of hypotheses and potential inferences to improve the health of the UK population.

2.3.2. Common and rare phenotypes and diseases

The size of this sample frame ambition will provide the ability to prospectively assess, with strong statistical precision, a wide range of common and rare phenotypes and diseases in a UK population. In addition, it will provide large numbers of prevalent diseases for retrospective, statistically powered case-control and case-cohort studies.

We have estimated incident diagnoses of disease that would accrue in Our Future Health in the initial 2.5-years of follow-up using various population/subpopulation sizes (**Appendix A**), demonstrating the immediacy of the impact that this programme will have on health research.

To interpret the advantages of these estimated incident diagnoses that may accrue in the population that comprises the Our Future Health cohort, we have also calculated minimal detectable odds ratios for aetiologic studies using ranges of case numbers, alpha values (critical p values), and exposure prevalence (**Table 2**). Note that the colour shading of all tables in these sample frame ambition sections indicates 0 cases (pure green), 5,000 cases (yellow), and 10,000 or more cases (red), a scale based on aetiologic odds ratios of ~1.5 for mid-range exposure prevalence and mid-range alphas.

²⁶ Nohr, E. A. and J. Olsen (2013). "Commentary: Epidemiologists have debated representativeness for more than 40 years--has the time come to move on?" *International Journal of Epidemiology* 42(4): 1016-1017.

²⁷ Schooling, C. M. and H. E. Jones (2014). "Is representativeness the right question?" *International Journal of Epidemiology* 43(2): 631-632.

²⁸ Huang, J. Y. (2021). "Representativeness Is Not Representative: Addressing Major Inferential Threats in the UK Biobank and Other Big Data Repositories." *Epidemiology* 32(2): 189-193.

Table 2. Minimal Detectable Odds Ratios by Case Count, Exposure Prevalence, and Critical p-value

Exposure Prevalence ^a	Critical p-value	Minimum detectable odds ratio, by number of cases ^b						
		500	1,000	2,500	5,000	7,500	10,000	25,000
0.5	0.05	1.28	1.19	1.12	1.08	1.07	1.06	1.04
0.5	0.00005	1.62	1.40	1.24	1.16	1.13	1.11	1.07
0.5	0.00000005	1.89	1.56	1.32	1.22	1.17	1.15	1.09
0.25	0.05	1.31	1.22	1.13	1.09	1.08	1.07	1.04
0.25	0.00005	1.65	1.44	1.26	1.18	1.15	1.13	1.08
0.25	0.00000005	1.90	1.59	1.35	1.24	1.19	1.17	1.10
0.1	0.05	1.45	1.31	1.19	1.13	1.11	1.09	1.06
0.1	0.00005	1.92	1.62	1.38	1.26	1.21	1.18	1.11
0.1	0.00000005	2.25	1.83	1.50	1.35	1.28	1.24	1.15
0.025	0.05	1.88	1.60	1.37	1.26	1.21	1.18	1.11
0.025	0.00005	2.83	2.22	1.74	1.51	1.41	1.35	1.22
0.025	0.00000005	3.53	2.66	1.98	1.67	1.54	1.47	1.29
0.01	0.05	2.43	1.97	1.59	1.41	1.33	1.29	1.18
0.01	0.00005	4.08	3.02	2.19	1.82	1.66	1.56	1.35
0.01	0.00000005	5.35	3.78	2.61	2.09	1.87	1.75	1.46
0.0025	0.05	4.21	3.11	2.25	1.85	1.69	1.59	1.36
0.0025	0.00005	8.60	5.70	3.63	2.75	2.39	2.18	1.72
0.0025	0.00000005	12.32	7.76	4.65	3.38	2.88	2.59	1.95
0.001	0.05	6.80	4.67	3.10	2.41	2.12	1.96	1.59
0.001	0.00005	16.14	9.85	5.67	4.00	3.35	2.98	2.18
0.001	0.00000005	24.59	14.28	7.70	5.20	4.24	3.72	2.59

^a Exposure prevalence among controls.

^b Calculated at 80% power assuming 4 controls per case.

A variety of scenarios can be deduced from this flexible table set up. For example, the advantages of having a population of 1 million can be clearly seen for diagnoses such as transient ischaemic attack and ischaemic stroke, irritable bowel syndrome, cholecystitis, tinnitus, diabetic eye disease, uterovaginal prolapse, postmenopausal bleeding, septicaemia, migraine, peripheral neuropathy, dementia, and rosacea, all of which accrue 4,000–6,000 cases in this short term period of follow-up – a threshold that provides strong statistical precision for testing aetiologic hypotheses. An increase to 2 million participants sees many other diagnoses surpass a 4,000-case threshold in this short period of follow-up, including lung and bowel cancers, stroke, non-rheumatic mitral valve disorder, anal fissure, Barrett's oesophagus, blindness, obstructive and reflux uropathy, neuropathic bladder, agranulocytosis, spinal stenosis, rheumatoid arthritis, fibromatosis, polymyalgia rheumatica, chronic sinusitis, sleep apnoea, and pulmonary collapse. The diseases that can be researched with strong statistical precision is obviously increased further as the number of participants and thus case numbers increase. At 5 million participants, many rarer diseases accrue to sufficient numbers to provide for strong statistical precision for a range of hypotheses to be investigated. These tables underscore the benefits of progressing towards and reaching 5 million participants in being able to study both common and rare phenotypes and diseases. They also underscore the unique opportunities that Our Future Health will provide to the world research community.

Another important use of the Our Future Health cohort will be in developing and validating predictive models of health and disease status. This includes polygenic/integrative risk scores and biomarkers, which will be generated and returned to consenting participants as a primary objective of the programme. However, with the rapid growth and development of machine learning methods, in step with advances in computing power, there will be a broad interest in using the cohort to develop new predictive models of different types. The case numbers shown in Appendix A demonstrate the potential of Our Future Health for research into predictive models of health and disease as they provide for high precision for estimates of validation statistics such as sensitivity and specificity (Table 3).

Table 3. Margins of Error for Estimates of Sensitivity and Specificity by Case or Control Count.

Sensitivity or Specificity (%)	Margin of error ^a (%), by number of cases or controls ^b						
	500	1,000	2,500	5,000	7,500	10,000	25,000
50	4.4	3.1	2.0	1.4	1.1	1.0	0.6
70	4.0	2.8	1.8	1.3	1.0	0.9	0.6
80	3.5	2.5	1.6	1.1	0.9	0.8	0.5
90	2.6	1.9	1.2	0.8	0.7	0.6	0.4
95	1.9	1.4	0.9	0.6	0.5	0.4	0.3

^a Margin of error is half the width of a 95% confidence interval

^b Cases for sensitivity; controls for specificity

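### Table 2's detectable odds ratios rest on an undisclosed one-sided test and null-only variance; read two-sided, the stated 80% power is about 70–76%, and lower for rare exposures

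*Protocol*

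**What the plan says.** Section 2.3.2 of the protocol introduces Table 2 with the words "we have also calculated minimal detectable odds ratios for aetiologic studies using ranges of case numbers, alpha values (critical p values), and exposure prevalence". The table is titled "Minimal Detectable Odds Ratios by Case Count, Exposure Prevalence, and Critical p-value". It covers seven exposure prevalences (0.5 down to 0.001), three critical p-values (0.05, 0.00005, 0.00000005) and seven case counts (500 to 25,000).

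Its only method notes are footnote a, "Exposure prevalence among controls", and footnote b, "Calculated at 80% power assuming 4 controls per case". Nothing in the text, the column headings or the footnotes says whether the tests are one- or two-sided, or which variance was used.

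The surrounding text uses the table to interpret the projected case numbers. It ties the colour scale to odds ratios of about 1.5 for mid-range prevalence and alpha, and treats 4,000–6,000 cases as enough for strong precision.

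**The concern.** A reader who meets a critical p-value of 0.05 or 0.00000005 in an aetiologic or genome-wide setting will normally take it as two-sided. If the table was built one-sided, each printed odds ratio is smaller than the one a two-sided test can detect with the stated power.

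A second problem comes on top. Using the null variance for both terms of the power formula does little harm when the exposure is common. When the exposure is rare and the odds ratio is large, the variance under the alternative exceeds the null variance, and the shortcut overstates power.

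The text invites readers to work out their own scenarios from individual cells. The rows most affected are the rare exposures, which are among the reasons given for wanting a very large cohort.

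**Working it through.** **Inputs, all from section 2.3.2.** Power 80%; 4 controls per case; the three critical p-values; prevalence p0 among controls; n cases. Case prevalence follows as p1 = p0·OR / (1 + p0(OR − 1)), and pooled prevalence as p̄ = (p1 + 4p0)/5.

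**Variance terms.** SE0 = √[p̄(1 − p̄)(1/n + 1/4n)] under the null; SE1 = √[p1(1 − p1)/n + p0(1 − p0)/4n] under the alternative.

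**Step 1: reproduce the table.** Each cell was solved for the odds ratio giving 80% power.

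| Form | Cells matched to two decimals |
|---|---|
| One-sided, SE0 only: Φ[(p1 − p0)/SE0 − z(1−α)] | 147 of 147 |
| One-sided, SE0 and SE1 | 54 of 147 |
| Two-sided, SE0 only | 17 of 147 |
| Two-sided, SE0 and SE1 | 13 of 147 |

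The largest gap for the first form is 0.005, which is rounding. Eleven variance forms were tried, one- and two-sided, with 1, 3, 4 or 5 controls per case. The next best matched 76 cells, and no two-sided form matched more than 55.

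Example, prevalence 0.5, 500 cases, printed OR 1.28: p1 = 0.64/1.14 = 0.5614; p̄ = 0.5123; SE0 = 0.02499; (p1 − p0)/SE0 = 2.457. One-sided: 2.457 − 1.645 = 0.812, power 79%. Two-sided: 2.457 − 1.960 = 0.497, power 69%. At the unrounded OR of 1.284 these are 80% and 70%.

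**Step 2: two-sided power, null variance kept.** At any unrounded tabulated OR, power is Φ[z(1−α) + 0.842 − z(1−α/2)]:

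- p = 0.05: 1.645 + 0.842 − 1.960 = 0.527, power 70.1%
- p = 0.00005: 3.891 + 0.842 − 4.056 = 0.677, power 75.1%
- p = 0.00000005: 5.327 + 0.842 − 5.451 = 0.717, power 76.3% (summed before rounding)

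Holding the odds ratio fixed, the cases needed rise by [(z(1−α/2) + 0.842)/(z(1−α) + 0.842)]², which is 1.27, 1.07 and 1.04.

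**Step 3: add the alternative variance.** Power = Φ{[(p1 − p0) − z·SE0]/SE1}. Example, prevalence 0.001, 5,000 cases, p = 0.05, OR 2.41: p1 − p0 = 0.0014066; SE0 = 0.0005656; SE1 = 0.0007281.

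- Plan's form: 0.0014066/0.0005656 − 1.645 = 0.842, power 80%.
- Two-sided with SE1: (0.0014066 − 1.960 × 0.0005656)/0.0007281 = 0.409, power 65.9%. Exact enumeration of the two-sided pooled z test gives 65.5%.
- One-sided with SE1: 74.3%. So in this row even the one-sided claim falls short of 80%.

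Across the prevalence 0.001 row at p = 0.05, two-sided power runs from 62.8% (500 cases) to 67.9% (25,000 cases).

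**Step 4: detectable odds ratios at 80%, two-sided, SE0 and SE1.**

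| Prevalence | Cases | Critical p | Printed | Recomputed |
|---|---|---|---|---|
| 0.025 | 5,000 | 0.00005 | 1.51 | 1.54 |
| 0.1 | 5,000 | 0.00005 | 1.26 | 1.27 |
| 0.5 | 500 | 0.05 | 1.28 | 1.32 |
| 0.01 | 5,000 | 0.05 | 1.41 | 1.49 |
| 0.001 | 5,000 | 0.05 | 2.41 | 2.80 |
| 0.001 | 5,000 | 0.00005 | 4.00 | 4.46 |
| 0.001 | 500 | 0.05 | 6.80 | about 10.0 |

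The median change over all 147 cells is 2.6%, and 65% of cells move by less than 5%.

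**Step 5: Table 4.** For a fixed design, ln(OR) at p = 0.00005 divided by ln(OR) at p = 0.05 should be near (4.056 + 0.842)/(1.960 + 0.842) = 1.75 if two-sided, and (3.891 + 0.842)/(1.645 + 0.842) = 1.90 if one-sided. Table 4 gives ln 1.57/ln 1.30 = 1.72; Table 2 gives ln 1.62/ln 1.28 = 1.95 and ln 1.26/ln 1.13 = 1.89. Direct attempts to reproduce Table 4 matched at most 19 of 96 cells.

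**The case against.** The strongest reply is that footnote b is true under the formula used, and that the protocol never says researchers will test two-sided. That stands: the 70–76% figures depend on the conventional reading, and what is shown unconditionally is an undisclosed and favourable basis. It does not rescue the rare-exposure rows, where the null-variance shortcut loses power even one-sided.

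Second, the cells the text leans on hardly change. The 5,000-case, mid-range cell is still about 1.5, and for prevalence 0.1 or more the largest change in any cell is 5.2%. This also stands, and it limits the severity.

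Third, the most dramatic cell (6.80 becoming about 10.0) is a corner. At OR 6.80 about 500 × 0.00676 = 3.4 exposed cases and 2,000 × 0.001 = 2 exposed controls are expected, so normal approximations are poor. Exact two-sided power there is 67% by a score test whose true size is about 8.2%, and 52% by the conservative Fisher test. The 5,000-case cells are the fairer illustration.

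A reader might also infer that Table 4 is two-sided and that the two tables therefore contradict each other. Its alpha scaling points that way, but its calculation could not be reproduced on either basis, so the documents do not establish it.

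**Conclusion.** The concern holds as a moderate correction. The one-sided, null-variance basis of Table 2 is identified by all 147 cells, and it is not disclosed. Assuming two-sided testing, the stated 80% is 70.1%, 75.1% and 76.3% at the three critical p-values. These figures apply to the unrounded odds ratios; power at printed values scatters around them. For prevalence 0.001 at p = 0.05 it is about 63–68% with the alternative variance.

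A reader might conclude that the case for 5 million participants falls with the table. It does not. The conclusions in the text are qualitative, the benchmark cell barely moves, and larger detectable odds ratios argue for more participants rather than fewer. The practical harm is to anyone who looks up a rare-exposure cell and takes its 80% at face value.

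**What to change.** Recompute Table 2 with two-sided critical values and a variance that uses p1 and p0 under the alternative, with exact power where expected exposed counts are small. State in footnote b that the tests are two-sided, and name the method. Labelling the present table one-sided would disclose the critical value but would leave the rare-exposure rows optimistic.

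Confirm from the original calculation whether Table 4 is one- or two-sided, state it, and put both tables on one basis.

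The cost is about an hour of recalculation for Table 2 and a replacement table, plus the Table 4 check. The detectable odds ratios become slightly less favourable for common exposures and visibly so for rare ones. On these figures the colour scale and the narrative argument need no change.
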